In our pilot study, immunoreactivity for CD274 was detected in the cytoplasm and cell membrane while CD273 and CD279 expression was observed in the cytoplasm. Scoring for CD274, CD273 will be semi-quantitative/ordered categorical. The percentage of the tumor cells staining positive for CD274, CD273 and the intensity of the tumor cells will be recorded as 0 (no staining), 1 (weak staining), 2 (moderate staining) and 3 (intense staining). Absolute CD279 positive cells will be counted under microscope lens x 20 power field. Representative 5 areas will be chosen to count. The average number from 5 areas will be recorded and be compared with data from image analysis.

Figure shows the immunohistochemical staining of CD279, CD274 and CD273 in advanced melanoma.

Assay performance

The results will be obtained on retrospective data sets. Protocols of these three antibodies have been optimized, standardized to minimize staining variance. Positive control and negative controls were used and stained separately with each batch of slides. The IHC staining of three markers (CD274, CD273 and CD279) has been performed in two different labs by three different technicians on whole tissue sections of Hodgkin lymphomas, melanomas, lung cancers and renal cell carcinomas. Three readers were involved, confirming the good reproducibility of the assay. Tumor will be considered positive if >5% (CD274) (Topalian S, 2012) or 10% (CD273) of the tumor cell population demonstrates unequivocally staining, respectively. CD279 positivity was defined as >3% positive cells/HPF (Bachireddy P, 2013). Statistically, Fisher's Exact Test will be used to measure the association between CD274, CD273, CD27 expression and objective response

of patients. All p values will be two sided, and statistical significance will be set at $p<0.05$. All IHC stained slides will be evaluated and scored by a pathologist ([name]). A subset of slides will be reviewed by a second pathologist ([name]) to ensure concordance of interpretation.

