nivolumab and ipilimumab with a primary endpoint of objective response per RECISTS 1.1 among

For the primary endpoint of overall response with a null hypothesis of 5% and an alternative hypothesis of 30% we would need 25 patients in a two-stage design with 8 patients in the first stage and 17 patients in the second stage. At the first stage analysis we will assess overall response, we will need to observe at least 1 response out of 8 patients to continue through the second stage. At the second stage, we will assess overall response rate again, and we will need to observe at least 3 responses out of 25 patients to accept the treatment. The overall power for overall response rate is 94%. The overall type I error, the chance of incorrectly rejecting the null hypothesis is 9%. The probability of stopping at the first stage under the null hypothesis is 66%. The operating characteristics of this design are calculated using the exact binomial distribution.

Subjects who continue treatment beyond initial investigator-assessed, RECIST 1.1-defined progression will be considered to have investigator-assessed progressive disease at the time of the initial progression event but may be designated as delayed responses for purposes of determining ORR and counted as responses for two stage designs.

In order to assess the impact of immune checkpoint inhibition in this population, tissue will be acquired to analyze the integrated biomarkers and determine the potential drug effect in this disease. Biomarkers will be assessed from pre-treatment and post-treatment biopsies collected in a minimum of 10 patients on this study. During enrollment to Cohort A, one set of pre-treatment and post-treatment biopsies was collected; the additional 9 were not performed because the study did not progress to Stage II. In Cohort B, paired immediate pre-treatment and post-treatment biopsies will be collected in the first eight participants who enroll to the study (stage 1-Cohort B). For this cohort, participants are required to have disease that can be biopsied safely, as discussed in Section 3.1.11. Biopsies will be optional among participants enrolled in the second stage of cohort B.

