In addition, we will explore the relationship between integrated biomarkers PDL1/PD1/PD2 status (PDL1 status, PDL1 in infiltrating lymphocytes, PD2 status in archival tumor) and response to combination treatment of nivolumab and ipilimumab. We will use Fisher's Exact Test to assess the relationship between each biomarker and response to combination treatment of nivolumab and ipilimumab. Each is expected to have similar characteristics. For example, with this design, assuming tissue is available on 90% of the sample, the probability of concluding combination treatment of nivolumab and ipilimumab response is related to the exploratory biomarker is 80%; given the unknown true response is 55% and 4% in positive marker versus negative marker patients, respectively, assuming 33% of the population is over-expressed for PDL1. The power to detect the relationship of interest increases as the prevalence of the biomarker increases. The operating characteristics of this design are calculated using a two-sided exact test with 10% type I error.

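### Section 13.4 says, without limit, that biomarker power rises with marker prevalence; under its own inputs power peaks near 45-47% prevalence and then falls, so the 80% cannot be carried to every marker

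*Combined protocol and SAP*

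**What the plan says.** Section 13.4 (Cohort B) plans one test per marker: "We will use Fisher's Exact Test to assess the relationship between each biomarker and response to combination treatment of nivolumab and ipilimumab". It illustrates power with a single case, giving 80% under these conditions:

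- "assuming tissue is available on 90% of the sample"
- PD-L1 positivity in 33% of patients
- "given the unknown true response is 55% and 4% in positive marker versus negative marker patients, respectively"
- a two-sided exact test at 10%.

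Two general statements surround the example. Of the markers as a group it says "Each is expected to have similar characteristics". Of prevalence it says "The power to detect the relationship of interest increases as the prevalence of the biomarker increases", with no upper limit.

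The sample comes from Section 13.1: "we would need 25 patients in a two-stage design with 8 patients in the first stage and 17 patients in the second stage".

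Section 9.1.1.1 defines positivity differently for each marker: above 5% of tumor cells for CD274 (PD-L1), 10% of tumor cells for CD273 (PD-L2), and for PD-1, "CD279 positivity was defined as >3% positive cells/HPF". The same section plans Fisher tests of these markers against objective response at two-sided p<0.05.

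**The concern.** The power of a two-group comparison is limited by the smaller group. With 22 or 23 patients, raising prevalence helps while marker-positive patients are the minority. Once they are a clear majority, few marker-negative patients remain and power must fall. A statement that power rises with prevalence, without limit, therefore cannot hold for this design.

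The example is worked for PD-L1 only, and the plan then expects the other markers to behave alike without giving a prevalence for them. A reader could take 80% as a floor for any marker at least as common as 33%, and give a non-significant result more weight than it deserves. The relationship of these markers is listed as a secondary objective in Section 1.2, and Section 9.1.1.1 says PD-L1 results may inform stratification in later phase II trials.

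**Working it through.** **Inputs.** From Sections 13.1 and 13.4: 25 patients; tissue on 90%, so 0.90 × 25 = 22.5, taken as n = 22 or 23; response 55% in marker-positive and 4% in marker-negative patients; Fisher's exact test, two-sided, alpha 0.10.

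**Formula.** For k marker-positive patients,

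Power(k) = Σ Bin(a; k, 0.55) × Bin(c; n−k, 0.04),

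summed over all tables (a responders of k, c responders of n−k) with two-sided Fisher p ≤ 0.10. The marker count is random, so

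Power(prevalence) = Σ Bin(k; n, prevalence) × Power(k).

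**The plan's own figure.** At 33% prevalence this gives 79.8% (n = 22) and 81.9% (n = 23). A fixed split of 8 positive and 15 negative gives 80.1%. The stated 80% is reproduced.

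**Other prevalences, same inputs.** Overall response is 4% + 51% × prevalence.

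| Prevalence | Power, n = 22 | Power, n = 23 | Implied overall response |
|---|---|---|---|
| 20% | 67.7% | 69.2% | 14% |
| 33% | 79.8% | 81.9% | 21% |
| 40% | 82.1% | 84.7% | 24% |
| 45% | 82.5% (peak) | 85.5% | 27% |
| 50% | 81.9% | 85.3% | 30% |
| 60% | 77.0% | 81.2% | 35% |
| 67% | 69.4% | 74.0% | 38% |
| 75% | 56.0% | 59.7% | 42% |
| 80% | 44.8% | 47.5% | 45% |
| 90% | 16.3% | 18.1% | 50% |

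For n = 23 the maximum is at 47% prevalence, also 85.5%. Power is about 80% or more from 33% to about 55% prevalence for n = 22, and from 30% to about 62% for n = 23.

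**Why it falls.** Compare two splits by hand.

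- 8 positive, 15 negative: 3 responders, all positive, are enough, with p = C(8,3)/C(23,3) = 56/1771 = 0.032. The expected number of positive responders is 8 × 0.55 = 4.4.
- 18 positive, 4 negative: 9 responders, all positive, are not enough. The two-sided p is [C(13,4) + C(9,4)]/C(22,4) = (715 + 126)/7315 = 0.115. Ten are needed: (495 + 210)/7315 = 0.096. The expected number is 18 × 0.55 = 9.9, so the test succeeds about half the time; enumeration gives 49.7%.

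**Sensitivity.**

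- Tissue on all 25: the peak is 89.0% near 47% prevalence, and power at 80% prevalence is 55.4%. The decline remains; the fall below 50% at 80% prevalence is specific to 22-23 patients.
- Alpha 5% (the threshold in Section 9.1.1.1): 69.6%/72.8% at 33% prevalence and 26.6%/33.0% at 80%.
- Counting a stage 1 stop (0 of 8 responders) as no rejection: 70%/72% at 33% prevalence, a peak near 50%, and 45%/47% at 80%.
- Response 40% against 4%: about 45% to 60% power across 33-60% prevalence.

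**The case against.** The strongest reply is that the sentence follows a 33% example and is true there: power does rise from low prevalence to about 45%. The steepest losses also lie outside the trial's design range. Holding 55% against 4% fixed, 80% prevalence implies an overall response of about 45%, while Cohort B's design alternative is 30%, reached at about 51% prevalence. Between 33% and 51% prevalence power stays at 79.8-82.5% (n = 22) or 81.9-85.5% (n = 23). The only observed PD-L1 prevalence in the documents is 38% (21 of 56, melanoma, Section 2.2.1.2.4). The remark about similar characteristics can be read as assuming a similar prevalence for each marker. Section 13.4 calls its figure an example, and Section 9 labels PD-1 and PD-L2 staining exploratory.

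All of this stands, and it limits the consequence. It does not rescue the sentence, which has no upper limit. From 33% to the peak power gains only about 3 to 4 points, whereas from the peak to 80% prevalence it loses about 38. If similar prevalence is assumed, the plan does not say so.

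Some stronger inferences are tempting and not supported:

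- That PD-1 or PD-L2 is in fact common in this disease and its test underpowered. No prevalence is documented for either, and different cut-offs do not establish one.
- That the plan will report a non-significant test as evidence of no association. No section says this.
- That a non-significant result is conclusive when prevalence lies in the favourable band. Power there depends on a 51-point difference in response.

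**Conclusion.** The point holds as an error in a stated power property. The 80% at 33% prevalence is right. The claim that power increases with prevalence is right only up to about 45-47%; beyond that it is wrong, with power of 77%/81% at 60% prevalence, 45%/48% at 80% and 16%/18% at 90%. Without a stated prevalence for PD-1 and PD-L2, the 80% cannot be extended to them.

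These figures rest on the plan's own assumptions: 22 or 23 patients with tissue, full enrolment, 55% against 4%, and a two-sided 10% test, with the marker count treated as random. The size of the fall depends on them; its direction was the same in the variants checked with all 25 patients, at 5% alpha and allowing for the stage 1 stop. The conflict between 10% in Section 13.4 and p<0.05 in Section 9.1.1.1 matters separately, because at 5% the worked example has 70-73% power rather than 80%.

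The practical effect is confined to interpretation of the biomarker tests. The two-stage response decision does not use them.

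**What to change.** In Section 13.4:

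1. Limit the prevalence sentence to values up to about 45%, or replace it with a short table of power by prevalence, noting that power is about 80% or more only for roughly 33-55% and lower on both sides.
2. State that the 80% applies to another marker only if its prevalence and its difference in response are similar to the PD-L1 example.
3. State that the figures assume full enrolment and a 55% against 4% difference.
4. Reconcile the 10% level with the p<0.05 in Section 9.1.1.1, and compute the power figures at the level that will be used.

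The cost is a wording change and one recalculation, with no effect on sample size, conduct or the primary analysis. The stated power becomes less favourable for common and for rare markers, and for every marker if the 5% level is kept.

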1.2 Secondary Objectives

Secondary Objectives:

- To evaluate the toxicity of nivolumab in patients with advanced ULMS.
- To evaluate the toxicity of nivolumab in combination with ipilimumab in patients with advanced ULMS.
- To evaluate the progression-free survival of ULMS treated with nivolumab.
- To evaluate the progression-free survival of ULMS treated with nivolumab in combination with ipilimumab.
- To explore the relationship between PDL1, PD1 in infiltrating lymphocytes and PD2 status in archival tumor, and pre/post treatment biopsies in a minimum of 10 patients.

Exploratory Objectives:

- To explore the relationship between general immune response and specific markers of immunomodulation and response to nivolumab.
- To explore the relationship between tumor inflammatory gene signature and response to nivolumab in archival material.

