
2.6 Correlative Studies Background

Nivolumab was initially thought to be most effective in tumors which express PDL1, a marker that may vary in a variety of tumor samples over time, however, with increased experience with this agent, it appears that both PDL1 and nonPDL1 expressing tumors may benefit from nivolumab, either as a single agent or in combination with ipilimumab. Development of biomarkers for response to nivolumab remain under active investigation and are a critical aspect to study design.

We aim to explore the relationship between ORR and PFS to general immune response (CD3, CD4, CD8, FOX-P3, CD68, CD63) as well as more specific markers of immunomodulation including PD-1, PDL-1, PDL-2. We hypothesize that the expression of these markers, either alone or in combination, may lead to the identification of a subset

of patients with ULMS who are more likely to respond to nivolumab. This evaluation will be performed on archival tumor material for all participants when available, and in paired pre/post-treatment biopsies in up to 10 participants. In addition, we have extensive experience using digital scanning of pathology slides and using image analysis to quantify immune infiltrates which will be applied to this cohort and related to response (14). This work will be performed under the direction of [name], PhD and at the Center for Immuno-oncology Pathology Core at Dana Farber–Harvard Cancer Center housed in the Specialized Histopathology Core at the Brigham and Women’s Hospital. The immuno-oncology core at Dana-Farber Harvard Cancer Center (DFHCC) has optimized IHC for these markers (Chen *et al*, 2013) and is actively developing IHC for IDO.

The immuno-oncology core lab at DFHCC evaluation of gene expression profiling with the aim of identification of an immune gene signature with the goal of identify patients more likely to respond to therapy with immune checkpoint inhibitors. Therefore, when material is available, we plan to evaluate targeted expression profiling for immune response signature on FFPE using nanostring platform at the immuno-oncology core at DFHCC (Scott *et al*, 2014).

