3.1.9 The effects of nivolumab on the developing human fetus are unknown. For this reason women of child-bearing potential (WOCBP) must agree to use adequate contraception (hormonal or barrier method of birth control; abstinence) prior to study entry and for the duration of study participation. WOCBP should use an adequate method to avoid pregnancy for 31 weeks after the last dose of investigational drug. Women of childbearing potential must have a negative serum or urine pregnancy test (minimum sensitivity 25 IU/L or equivalent units of HCG) within 24 hours prior to the start of nivolumab. Women must not be breastfeeding. Women who are not of childbearing potential (*i.e.*, who are postmenopausal or surgically sterile) do not require contraception.

Women of childbearing potential (WOCBP) is defined as any female who has experienced menarche and who has not undergone surgical sterilization (hysterectomy or bilateral oophorectomy) or who is not postmenopausal. Menopause is defined clinically as 12 months of amenorrhea in a woman over 45 in the absence of other biological or physiological causes. In addition, women under the age of 55 must have a documented serum follicle stimulating hormone (FSH) level less than 40 mIU/mL.

WOCBP receiving nivolumab will be instructed to adhere to contraception for a period of 31 weeks after the last dose of investigational product. These durations have been calculated using the upper limit of the half-life for nivolumab (25 days) and are based on the protocol requirement that WOCBP use contraception for 5 half-lives plus 30 days.

Should a woman become pregnant or suspect she is pregnant while participating in this study, she should inform the treating physician immediately.

The effects of nivolumab on the developing human fetus are unknown.

- 3.1.10 Ability to understand and the willingness to sign a written informed consent document.
- 3.1.11 For enrollment in the first stage of Cohort B, patients must have accessible pre-treatment and post-treatment (4-6 weeks) tumor for biopsy.

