9.1.1.1 Collection of Specimen(s)

Assay, patient and specimen information

Immunohistochemical (IHC) staining of CD274 will be used as an integrated biomarker in this clinical trial, and to identify a group of patients most likely to respond to the immune checkpoint inhibition with nivolumab or nivolumab and ipilimumab. This information may be used in the future phase II trials as a stratification variable. IHC staining of CD273, CD279 will also be performed as exploratory biomarkers to explore a possible relationship between expression and response to nivolumab or nivolumab and ipilimumab in this population. Pre-treatment archival tumor material will be collected for all eligible patients. In addition, because expression of these markers may change over time, paired immediate pre-treatment and post-treatment biopsies will be obtained in all patients enrolled to Cohort B. In Cohort A, pre-treatment archival tumor material was collected for ten out of the twelve patients treated. In Cohort A, paired biopsies were not required for all participants; one set of paired biopsies was conducted. These paired biopsies will

be collected and fixed by 10% neutral buffered formalin overnight, dehydrated and paraffin embedded. Four-micrometer-thick sections will be cut. The paraffin blocks and unstained slides will be stored at room temperature. All IHC staining will be performed in the Center for Immuno-Oncology Pathology Core at Dana-Farber/Harvard Cancer Center Specialized Histopathology Core, which will be a central research laboratory for this multiple-center clinical trial. Unstained slides from other two centers will be shipped to [name], [name], Brigham and Women Hospital, [name].

Primary antibody characteristics

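### The marker-response Fisher test has two significance levels (p<0.05 in 9.1.1, 10% in 13.4, where the 80% power is computed); separately, the rules on who has paired biopsies, and how many, conflict

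*Combined protocol and SAP*

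**What the plan says.** **Marker test.** Section 9.1.1.1, under Assay performance, says Fisher's exact test "will be used to measure the association between CD274, CD273, CD27 expression and objective response" of patients. It adds: "All p values will be two sided, and statistical significance will be set at $p<0.05". Section 13.4 (Cohort B) uses Fisher's exact test for each of the PD-L1, PD-1 and PD-L2 markers against response to the combination. It states that "the probability of concluding combination treatment of nivolumab and ipilimumab response is related to the exploratory biomarker is 80" per cent, and then: "The operating characteristics of this design are calculated using a two-sided exact test with 10% type I error". The inputs there are response rates of 55% (marker-positive) and 4% (marker-negative), 33% prevalence, and tissue on 90% of the sample.

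**Paired biopsies, how many.** Section 1.2 says "pre/post treatment biopsies in a minimum of 10 patients", and Section 13.1 repeats that minimum for the study. Section 2.6 says "in paired pre/post-treatment biopsies in up to 10 participants".

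**Paired biopsies, from whom.** Section 3.1.11 says "For enrollment in the first stage of Cohort B, patients must have accessible pre-treatment and post-treatment (4-6 weeks) tumor for biopsy". Section 13.1 collects pairs from the first eight Cohort B participants and makes biopsies optional in stage 2. Section 9.1.1.1 says "paired immediate pre-treatment and post-treatment biopsies will be obtained in all patients enrolled to Cohort B", and footnote d of the Cohort B calendar in Section 10 also requires them of every participant. Cohort A closed with one pair.

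**The concern.** The two sections name the same test, the same markers (Section 9.1.1 identifies CD274 as PD-L1, CD273 as PD-L2 and CD279 as PD-1) and the same outcome, but different thresholds. With both on file, the level could be chosen after the p-value is known. No stopping or treatment decision uses this p-value. It does decide what is reported for an objective that Section 1.2 lists as secondary, and Section 9.1.1.1 says the PD-L1 result may be used to stratify later phase II trials.

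The biopsy conflict is a different matter and is not an input to the power figure. It leaves a site unable to tell whether a stage 2 patient must have two biopsies. It also leaves the study with a minimum that it may be unable to meet.

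**Working it through.** **Inputs.** From Section 13.4: response 55% versus 4%, prevalence 33%, tissue 90%, two-sided 10%. From Section 9.1.1.1: two-sided 0.05. From Section 13.2: Cohort B has 25 patients (8 + 17). Since 0.90 × 25 = 22.5, I assume N = 22 or 23. Expected marker-positive patients are 0.33 × 22 = 7.3 or 0.33 × 23 = 7.6, so I take fixed counts of 7 and 8, and also average over a Binomial(N, 0.33) count.

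**Method.** For n₁ marker-positive and n₂ marker-negative patients, power is the sum of Bin(a; n₁, 0.55) × Bin(b; n₂, 0.04) over all pairs (a, b) whose two-sided Fisher p is at or below the level.

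| Marker-positive / negative | Power at 10% | Power at 0.05 | Chance that 0.05 < p ≤ 0.10 |
|---|---|---|---|
| 8 / 15 | 80.1% | 79.6% | 0.5% |
| 8 / 14 | 80.8% | 78.1% | 2.7% |
| 7 / 16 | 86.9% | 72.5% | 14.5% |
| 7 / 15 | 87.6% | 69.9% | 17.8% |
| averaged, N = 22 | 79.8% | 69.6% | 10.3% |
| averaged, N = 23 | 81.9% | 72.8% | 9.1% |

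The last column is the difference between the two power columns, taken before rounding.

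The plan's 80% is reproduced at 10% by 8/15, 8/14 and the average at N = 22. The loss at 0.05 depends strongly on the split because Fisher's test is discrete.

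**A result that the two sections would report differently.** Take 3 of 7 marker-positive and 1 of 15 marker-negative responders, 4 responders in 22. The number of ways to place 4 responders among 22 is C(22,4) = 7315.

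- Exactly 3 marker-positive: C(7,3) × 15 = 525 ways.
- All 4 marker-positive: C(7,4) = 35 ways.
- In the other tail, 0 marker-positive has C(15,4) = 1365 ways. That is more likely than the observed table, so it does not count.

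Hence p = (525 + 35)/7315 = 0.077: significant under 13.4, not under 9.1.1.

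**Biopsies.**

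| Section | Who in Cohort B | How many |
|---|---|---|
| 1.2 | not stated | at least 10 |
| 2.6 | not stated | at most 10 |
| 3.1.11 | accessible tumor needed for stage 1 | not stated |
| 9.1.1.1 and calendar footnote d | everyone | not stated |
| 13.1 | stage 1; optional in stage 2 | at least 10 |

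- Stop after stage 1: 1 (Cohort A) + 8 = 9 pairs at most, under either rule.
- Full accrual, stage 1 mandatory only: 1 + 8 = 9 pairs assured; a tenth needs a stage 2 volunteer.
- Full accrual, everyone mandatory: 1 + 25 = 26.

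The probability of a stage 1 stop is 0.95⁸ = 0.663 under the 5% null, matching the 66% in Section 13.1. Under the 30% alternative it is 0.70⁸ = 0.058.

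**The case against.** **The two levels may belong to different analyses.** Section 9.1.1 makes PD-L1 by the DAKO kit the integrated biomarker and runs in-house antibody staining in parallel for exploratory comparison. The p<0.05 sentence follows the antibody description, in a paragraph that opens with retrospective data. On that reading 0.05 is the laboratory's rule and 10% the design's. This does not hold: for PD-1 and PD-L2 the plan describes only the in-house antibodies, and Section 13.4 tests those markers too. Section 9.1.1.1 also refers prospectively to patients' objective response.

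**The 10% may be only a planning figure.** Section 13.4 says the operating characteristics are calculated at 10%; it does not call that a reporting threshold. But the 80% is given as the probability of concluding that there is a relationship, so the level is the rule for concluding.

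**The large losses come from splits that do not give 80%.** This stands in part. The 7-positive splits give about 87% at 10%. Of the fixed splits that do give 80%, 8/15 loses 0.5 points and 8/14 loses 2.7, so if 8/15 was used, 80% survives rounding at 0.05. The example also depends on the split: 3/8 versus 1/15 gives p = (840 + 70)/8855 = 0.103, negative under both rules. However, the average at N = 22 also gives 80% and falls to 69.6%, and the text does not say which calculation was done. The conflict over the threshold does not depend on the power loss.

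**The biopsy shortfall is one pair for a descriptive aim.** True, and a stage 1 stop is unlikely if the treatment works as assumed. The mandatory-versus-optional contradiction remains.

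**Conclusion.** Both parts hold. The 80% in Section 13.4 is not an arithmetic error; it is correct at the 10% named there. Under the 0.05 rule of Section 9.1.1 it does not generally hold: about 70% to 73% averaged over the marker-positive count, and 70% to 80% for fixed counts of 7 or 8. The probability of a p-value on which the two sections disagree is 9% to 10% on average under the assumed effect, ranging from 0.5% to 17.8% by split. These figures assume N = 22 or 23, full accrual of 25, and the response rates and prevalence in Section 13.4.

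The biopsy sections contradict each other on stage 2 of Cohort B and on whether 10 is a floor or a ceiling. The stated minimum of 10 cannot be reached after a stage 1 stop, when at most 9 pairs exist. The textual conflicts are certain; the exact power under 0.05 is not, because the split is unstated. This should be corrected, but it does not affect the primary endpoint.

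**What to change.** 1. State one significance level for the marker-response Fisher test in both 9.1.1 and 13.4. Either carry 10% into 9.1.1 and keep the 80%, or use 0.05 in both and restate power as about 70% to 73% (70% to 80% by split). In either case give the number of patients with tissue, state whether the marker split is fixed or averaged and at what values, and note that the power applies to full accrual of 25.
2. Reconcile Sections 1.2, 2.6, 3.1.11, 9.1.1.1, 10 (Cohort B, footnote d) and 13.1 on who must have paired biopsies and on whether 10 is a minimum or a maximum. Then restate the minimum as a number that the reconciled rule can deliver, including after a stage 1 stop (at most 9).

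The cost is wording and restated figures, with no extra patients. If the sponsor resolves the second point towards all of Cohort B, Section 3.1.11 would have to be extended, and biopsies would be mandatory for up to 17 stage 2 patients for whom Section 13.1 now makes them optional.
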